14.3.1.3 Ratios and Confidence Intervals

Ratios of LSMS will be calculated using the exponentiation of the difference between treatment LSMS from the analyses on the ln-transformed AUC0-t, AUC0-24 (for Part 2, Day 1 PK only), AUC0-inf, and Cmax. These ratios will be expressed as a percentage relative to the appropriate reference treatment.

Consistent with the two one-sided tests [Schuirmann, 1987], 90% confidence interval (CI) for the ratios will be derived by exponentiation of the CIs obtained for the difference between treatment LSMS resulting from the analyses on the ln-transformed AUC0-t, AUC0-24 (for Part 2, Day 1 only), AUC0-inf, and Cmax. The CIs will be expressed as a percentage relative to the appropriate reference treatment.

The comparisons of interest are as follows:

- Treatment B compared with Treatment A [Part 1]
- Treatment D (Day 1 dosing) compared with Treatment C [Part 2]
- Treatment D (Day 10 dosing) compared with Treatment C [Part 2]

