8.2.3 Rationale for Study Endpoints

The primary PK endpoints for Parts 1 and 2 will include AUC0-t, AUC0-24 (for Part 2, Day 1 PK only), AUC0-inf, and Cmax, as these parameters describe the exposure and bioavailability of LOXO-292 and are thought to be the most relevant PK parameters for the purpose of evaluating an interaction.

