10 STUDY DESIGN

10.1 Overall Study Design and Plan

This is a 2-part study. Each part will be conducted as an open label, 2-period, fixed-sequence study. Study parts may be conducted concurrently. Subjects will only participate in one study part.

CCI [REDACTED] healthy, adult male and female (women of non-childbearing potential only) subjects will be enrolled in total; CCI [REDACTED] to each study part (Parts 1 and 2). Every attempt will be made to enroll at least 4 subjects of each sex in each study part.

Screening of subjects will occur within 28 days prior to the first dosing.

Part 1 (Itraconazole):

On Day 1 of Period 1, a single oral dose of LOXO-292 will be administered followed by PK sampling for 168 hours.

In Period 2, an oral dose of itraconazole will be administered QD for 11 consecutive days (Day -4 to Day 7) with a single oral dose of LOXO-292 coadministered on Day 1. Pharmacokinetic sampling for LOXO-292 will be taken for 168 hours following LOXO-292 dosing on Day 1.

A CCI [REDACTED] will initiate Part 1; all subjects will receive a single dose of LOXO-292 on Day 1 of both periods. Following collection of the last PK sample in Period 2, the PI, in consultation with the Sponsor, will review all pertinent safety and tolerability data before proceeding to dose the remaining subjects.

Interim PK will be provided after completion of the sentinel group but it is not required for the dose selection of the remaining subjects.

There will be a washout period of at least 7 days between the dose in Period 1 and the first dose (i.e., itraconazole) in Period 2.

Safety will be monitored throughout the study.

Timing of all study procedures are indicated in the Study Events Flow Chart (Section 6, Table 1)

Part 2 (Rifampin):

On Day 1 of Period 1, a single oral dose of LOXO-292 will be administered followed by PK sampling for 168 hours.

In Period 2, an oral dose of rifampin will be administered QD for 16 consecutive days (Days 1 to 16) with a single oral dose of LOXO-292 coadministered on Day 1 and Day 10.

Pharmacokinetic sampling for LOXO-292 will be taken for 24 hours following LOXO-292 dosing on Day 1 and for 168 hours following LOXO-292 dosing on Day 10.

Morning urine will be collected on Days 1, 4, 8, and 10 of Period 2 (and will be stored for future potential assessment of 6 β -hydroxycortisol and free cortisol concentrations to evaluate the level of CYP3A enzyme induction).

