13.3.2 Plasma Pharmacokinetic Parameters

PK parameters for plasma LOXO-292 will be calculated as follows, as appropriate:

AUC0-24: The area under the concentration-time curve, from time 0 to the 24 hours postdose Day 1, as calculated by the linear trapezoidal method (for Part 2, Day 1 PK only).

AUC0-t:	The area under the concentration-time curve, from time 0 to the last observed non-zero concentration, as calculated by the linear trapezoidal method.
AUC0-inf:	The area under the concentration-time curve from time 0 extrapolated to infinity. AUC0-inf is calculated as the sum of AUC0-t plus the ratio of the last measurable plasma concentration to the elimination rate constant.
AUC%extrap:	Percent of AUC0-inf extrapolated, represented as $(1 - AUC0-t/AUC0-inf) * 100$.
Cmax:	Maximum observed concentration.
CL/F:	Apparent total plasma clearance after oral (extravascular) administration, calculated as Dose/AUC0-inf.
Tmax:	Time to reach Cmax. If the maximum value occurs at more than one time point, Tmax is defined as the first time point with this value.
Kel:	Apparent first-order terminal elimination rate constant calculated from a semi-log plot of the plasma concentration versus time curve. The parameter will be calculated by linear least-squares regression analysis using the maximum number of points in the terminal log-linear phase (e.g., three or more non-zero plasma concentrations).
t ^{1/2} :	Apparent first-order terminal elimination half-life will be calculated as $0.693/Kel$.

No value for Kel, AUC0-inf, or t^{1/2} will be reported for cases that do not exhibit a terminal log-linear phase in the concentration-time profile. The sampling to 24 hours for Day 1 PK in Period 2, Part 2 may not be sufficient for calculation of several Kel-dependent PK parameters.

No PK parameters will be calculated for subjects with 2 or fewer consecutive time points with detectable concentrations.

Individual and mean plasma concentration time curves (both linear and log-linear) will be included in the final report.

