14.3.1.2 Analysis of Variance

An ANOVA will be performed on the ln-transformed AUC0-t, AUC0-24 (for Part 2, Day 1 PK only), AUC0-inf, and Cmax. The ANOVA model will include treatment and period as fixed effects and subject as a random effect. Each ANOVA will include calculation of LSM as well as the difference between treatment LSMs.

In Part 1, data of the sentinel subjects will be included in the analysis if the same LOXO-292 dose (160 mg) was administered in the remaining subjects.

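### Part 2: the primary AUC0-t ratio for rifampin Day 1 versus LOXO-292 alone sets a 24 h window against one of up to 168 h, so it reads low when rifampin has no acute effect

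*Protocol*

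**What the plan says.** Section 8.2.3 sets the primary endpoints: "The primary PK endpoints for Parts 1 and 2 will include AUC0-t, AUC0-24 (for Part 2, Day 1 PK only), AUC0-inf, and Cmax". The parenthesis restricts AUC0-24; AUC0-t carries no restriction.

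Section 14.3.1.2 sends the same list into the model: "An ANOVA will be performed on the ln-transformed AUC0-t, AUC0-24 (for Part 2, Day 1 PK only), AUC0-inf, and Cmax". Section 14.3.1.3 then states: "Ratios of LSMS will be calculated using the exponentiation of the difference between treatment LSMS from the analyses on the ln-transformed AUC0-t" and the other parameters, with 90% CIs to match. Its contrasts for Part 2 are "Treatment D (Day 1 dosing) compared with Treatment C [Part 2" and the Day 10 equivalent. No parameter is tied to, or removed from, either contrast.

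Section 13.3.2 defines AUC0-t as the area "from time 0 to the last observed non-zero concentration, as calculated by the linear trapezoidal method", so the sampling schedule limits its upper end. Section 10.1 gives that schedule. In Period 1 (Treatment C), "a single oral dose of LOXO-292 will be administered followed by PK sampling for 168 hours". In Period 2 (Treatment D), samples are "taken for 24 hours following LOXO-292 dosing on Day 1 and for 168 hours following LOXO-292 dosing on Day 10".

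The one caution about the short Day 1 profile is in 13.3.2: it "may not be sufficient for calculation of several Kel-dependent PK parameters". AUC0-t does not depend on Kel, so this caution does not cover it.

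**The concern.** The acute effect of a single rifampin dose, through P-gp inhibition, is one of the two primary questions of Part 2 (section 9.1). Section 8.2.2 says the Day 1 dose is there to detect small PK differences. Inhibition would be expected to raise exposure.

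For this contrast the AUC0-t numerator stops at 24 h at the latest, while the denominator can run to 168 h. If rifampin does nothing, the numerator is only the first part of the denominator and the ratio must be below 100%. Followed as written, the protocol yields a primary ratio and 90% CI centred on a fall in exposure that did not happen. A real increase could be hidden or shown as a decrease. The same report would carry an AUC0-24 ratio that disagrees by construction, and the protocol does not say which of the two answers the question.

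**Working it through.** The protocol states no expected ratio, so there is no figure of its own to reproduce. The question is what the AUC0-t ratio would be with no rifampin effect.

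**Inputs**
- Half-life at least 12 h and possibly 30 h (8.2.1).
- Tmax about 2 h (8.1.1).
- Sampling at 0, 0.25, 0.5, 0.75, 1, 1.5, 2, 2.5, 3, 4, 6, 8, 12, 24, 48, 72, 96, 120, 144 and 168 h (section 6); D Day 1 stops at 24 h.
- Linear trapezoids (13.3.2).
- Assumed: a one-compartment profile, with Treatment C measurable to 168 h.

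**Direction.** With no effect,

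R = AUC0-24 / (AUC0-24 + AUC from 24 h to the last measurable time in C).

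This is below 1 whenever C has any measurable concentration after 24 h, whatever the shape of the curve.

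**Size.** C(t) is proportional to exp(−k·t) − exp(−ka·t), with k = ln 2 / t½ and ka solved from ln(ka/k)/(ka − k) = 2 h. Areas are in arbitrary units.

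| t½ | ka (per h) | AUC0-24 | AUC0-168 | No-effect ratio R | Break-even 1/R |
|---|---|---|---|---|---|
| 12 h | 1.769 | 12.59 | 17.59 | 0.716 | 1.40 |
| 24 h | 2.194 | 16.92 | 34.64 | 0.488 | 2.05 |
| 30 h | 2.330 | 18.03 | 42.61 | 0.423 | 2.36 |

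A hand check without the absorption phase, (1 − 2^(−24/t½)) / (1 − 2^(−168/t½)), gives 0.750, 0.504 and 0.435.

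**With a true effect.** A proportional increase of θ reads as θ·R. As a yardstick only, section 8.1.2 cites a rise of about 1.7-fold in digoxin AUC with itraconazole, attributed to P-gp. A true 1.7-fold increase would read as 1.7 × 0.716 = 122%, 1.7 × 0.488 = 83% or 1.7 × 0.423 = 72%. At the two longer half-lives the sign is wrong.

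**Sensitivity of R** (half-lives 12, 24 and 30 h)
- C measurable only to 72 h: 73%, 56%, 51%.
- C measurable only to 48 h: 77%, 65%, 62%.
- Fast distribution phase added (assumed fast half-life 2–4 h, 50–90% of the intercept), C measurable to 168 h: 74–90%, 51–76%, 45–71%. Break-even is 1.12–1.35, 1.31–1.94 and 1.42–2.24.
- Fast phase together with C measurable only to 48 h (weights applied to the disposition phases): about 80–92%, 68–86%, 65–85%.
- Period 1 drug remaining after a 7-day washout: at 30 h, R moves from 42.3% to 43.2%.

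**Matched measure.** With 0–24 h in both profiles the no-effect ratio is 100%. Allowing for residual Period 1 drug it is 100.0%, 100.8% and 102.1%.

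**AUC0-inf, a side point.** It has no window mismatch, but on D Day 1 the share beyond 24 h is 26%, 51% and 58% in the one-compartment case. With Kel from the last three points, its no-effect ratio is 0.96, 0.98 and 0.99. With the fast phase added it falls to about 0.92–0.95, 0.80–0.91 and 0.74–0.89, because a 24 h profile then overestimates Kel.

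**The case against.** The best reply is that no sentence names AUC0-t as the measure for D (Day 1) versus C; that reading comes from crossing a parameter list with a contrast list. AUC0-24 was added specifically for the Part 2 Day 1 profile, and 8.2.2 explains why 24 h is enough for the acute effect, so the authors very likely meant AUC0-24 to be the extent measure there. Parameters are calculated as appropriate (13.3.2), and section 14.3 leaves detailed methods to the SAP. No equivalence bound or decision rule hangs on the AUC0-t ratio, and a careful reader would see AUC0-24 and Cmax beside it. The size of the bias also rests on an assumed profile and an unstated assay limit.

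Part of this stands. The intention is probably sound, valid measures are already planned, and the size is uncertain: in the most favourable case examined, the no-effect ratio at 12 h reaches about 92%.

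The rest does not remove the problem. AUC0-t on Day 1 can be calculated, so the as-appropriate wording does not exclude it; it is simply not comparable with Treatment C. The lists in 8.2.3, 14.3.1.2 and 14.3.1.3 fix AUC0-t as primary without exception, and section 14.3 itself requires major changes to the primary analysis to go into a protocol amendment as well. Nor is it explicit that AUC0-24 will be derived for Treatment C, since the parenthesis can be read as meaning Period 2 Day 1 only.

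**Conclusion.** The concern holds. As written, the protocol prescribes a primary AUC0-t ratio and 90% CI for D (Day 1) versus C that compare unequal time windows. With no acute rifampin effect the ratio is too low in every case examined. It is 72% to 42% over half-lives of 12 to 30 h for a one-compartment profile measurable to 168 h, and at most about 92% under the most favourable assumptions tried. The downward direction requires only that LOXO-292 is measurable beyond 24 h in Treatment C, which the protocol expects given a half-life of at least 12 h. The size depends on the profile shape and the last measurable time, neither of which the protocol fixes.

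This should be fixed, but it does not undermine the study: AUC0-24 and Cmax can answer the question, and the Day 10 contrast has matching 168 h sampling schedules.

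**What to change.** In 14.3.1.2 and 14.3.1.3, state that D (Day 1) versus C is assessed on Cmax and AUC0-24, and that the Part 2 AUC0-t ratio is calculated only for D (Day 10) versus C. In 13.3.2, state that AUC0-24 is derived from the first 24 h of both the D Day 1 and the Treatment C profiles. Align the primary endpoint sentence in 8.2.3. Section 9.2 lists endpoints without contrasts and can stay, provided 14.3.1.3 carries the restriction.

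It would also be prudent not to treat AUC0-inf as primary for the Day 1 contrast. Where it can be estimated, report it descriptively with AUC%extrap.

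The cost is wording only. The 24 h sample is already scheduled in both profiles, AUC0-24 and Cmax are already planned, and no sampling or dosing changes.

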14.3.2 Interim Pharmacokinetic Analysis

Interim PK will be provided after completion of the sentinel group but it is not required for the dose selection of the remaining subjects.

14.3.3 Safety Analyses

All safety data will be populated in the individual CRFs. All safety data, including dosing dates and times will be listed by subjects.

AEs will be coded using the Medical Dictionary for Regulatory Activities (MedDRA[®]) and summarized by treatment for the number of subjects reporting the treatment emergent adverse event (TEAE) and the number of TEAEs reported. A by-subject AE data listing including verbatim term, coded term, treatment, severity, and relationship to treatment will be provided.

Safety data including ECGs, physical examinations, vital signs assessments, and clinical laboratory results will be summarized by treatment and point of time of collection.

Quantitative safety data as well as the difference to baseline, when appropriate, will be summarized using the appropriate descriptive statistics.

Concomitant medications will be listed by subject and coded using the WHO drug dictionary. Medical history will be listed by subject.

15 STUDY ADMINISTRATION

15.1 Ethics

15.1.1 Institutional Review Board

This protocol will be reviewed by the Advarra IRB, and the study will not start until the IRB has approved the protocol or a modification thereof. The IRB is constituted and operates in accordance with the principles and requirements described in the US Code of Federal Regulations (21 CFR Part 56). The IRB is compliant to International Council for Harmonisation (ICH) guidelines, and may be reached at:

Advarra IRB
[name]
[name]
[contact]

15.1.2 Ethical Conduct of the Study

This research will be carried out in accordance with the protocol, US Code of Federal Regulations, 21 CFR Parts 50, 56, and 312, the ethical principles set forth in the Declaration of Helsinki, GCP, and the ICH harmonized tripartite guideline regarding GCP (E6 Consolidated Guidance, April 1996).

15.1.3 Subject Information and Consent

The purpose of the study, the procedures to be carried out and the potential hazards will be described to the subjects in non-technical terms. Subjects will be required to read, sign and date an ICF summarizing the discussion prior to screening, and will be assured that they may withdraw from the study at any time without jeopardizing their medical care.

Subjects will be given a copy of their signed ICF.

15.2 Termination of the Study

Celerion reserves the right to terminate the study in the interest of subject welfare.

Sponsor reserves the right to suspend or terminate the study at any time.

15.3 Data Quality Assurance

Standard operating procedures are available for all activities performed at Celerion relevant to the quality of this study. Designated personnel of Celerion will be responsible for implementing and maintaining quality assurance (QA) and quality control systems to ensure that the study is conducted, and that data are generated, documented and reported in compliance with the study protocol, GCP and Good Laboratory Practice requirements as well as applicable regulatory requirements and local laws, rules and regulations relating to the conduct of the clinical study.

The Clinical Study Report will be audited by the QA department and the QA audit certificate will be included in the study report.

All clinical data will undergo a 100% quality control check prior to clinical database lock. Edit checks are then performed for appropriate databases as a validation routine using SAS® or comparable statistical program to check for missing data, data inconsistencies, data ranges, etc. Corrections are made prior to database lock.

15.4 Direct Access to Source Data/Documents

Celerion will ensure that the Sponsor, IRB and inspection by domestic and foreign regulatory authorities will have direct access to all study-related sites, source data/documents, and reports for the purpose of monitoring and auditing (ICH[E6] 5.1.2 & 6.10). In the event that other study-related monitoring should be done by other parties, they will be required to sign a confidentiality agreement prior to any monitoring and auditing.

15.5 Drug Supplies, Packaging and Labeling

The Sponsor will supply sufficient quantities of LOXO-292 capsules to allow completion of this study. Celerion will provide sufficient quantities of rifampin and itraconazole to allow completion of the study. The lot numbers and expiration dates (where available) of the study drugs supplied will be recorded in the final report.

Records will be made of the receipt and dispensing of the study drugs supplied. At the conclusion of the study, any unused study drugs will be retained by Celerion, returned to the Sponsor or designee, or destroyed, as per Sponsor instructions. Any remaining supplies that were purchased by Celerion will be destroyed. If no supplies remain, this fact will be documented in the pharmacy product accountability records.

15.6 Data Handling and Record Keeping

Celerion standard CRFs will be supplied. CRFs are printed off directly from the database. Each CRF is reviewed and signed by the PI.

All raw data generated in connection with this study, together with the original copy of the final report, will be retained by Celerion until at least 5 years after the last approval of a marketing application in an ICH region and until there are no pending or contemplated marketing applications in an ICH region or at least 5 years have elapsed since the formal discontinuation of clinical development of the investigational product. These documents should be retained for a longer period however if required by the applicable regulatory requirements or by an agreement with the sponsor. It is the responsibility of the Sponsor to inform the PI/Institution as to when these documents no longer need to be retained.

15.7 Report Format

According to the ICH Harmonized Tripartite Guideline (Organization of the Common Technical Document for the Registration of Pharmaceuticals for Human Use M4 and the

ICH M2 Expert Working Group), the final report will be written according to the ICH E3 Guideline (Structure and Content of Clinical Study Reports).

15.8 Publication Policy

All unpublished information given to Celerion by the Sponsor shall not be published or disclosed to a third party without the prior written consent of the Sponsor.

The data generated by this study are considered confidential information and the property of the Sponsor. This confidential information may be published only in collaboration with participating personnel from the Sponsor or upon Sponsor's written consent to publish the article.

SPONSOR Study No.: LOXO-RET-18014

Date of Final Protocol, Amendment 1: 22-May-2018

Date of Protocol Clarification Letter: 01-Jun-2018

A 2-Part, Open-Label, Fixed-Sequence Study to Evaluate the Effects of Multiple Doses of Itraconazole and Rifampin on the Single-Dose Pharmacokinetics of LOXO-292 in Healthy Adult Subjects

This Protocol Clarification Letter is being generated to confirm (as per Celerion Clinical Site internal processes) that rechecks for vital signs, liver function tests, amylase and lipase can be performed to confirm eligibility for the LOXO-RET-18014 Study.

Therefore, the following statement should be added and at the end of the inclusion criterion 4 (Section 11.1): "Rechecks of vital sign values, liver function tests, amylase, or lipase values outside the protocol specified ranges will be permitted up to two times to confirm eligibility for study participation at screening and check-in of Period 1. Subjects may be eligible for participation in the study based on rechecked values if the Investigator, with agreement from the Sponsor, feels that the results are not clinically significant, and will not impact study conduct."

The Final Protocol, Amendment 1, dated 22 May 2018, was not amended to incorporate these changes, therefore, this protocol clarification letter is being written.

PPD

Clinical Protocol

A 2-Part, Open-Label, Fixed-Sequence Study to Evaluate the Effects of Multiple Doses of Itraconazole and Rifampin on the Single-Dose Pharmacokinetics of LOXO-292 in Healthy Adult Subjects

Celerion Project No.: CA24333

Sponsor Project No.: LOXO-RET-18014

US IND No.: 133193

GCP Statement

This study is to be performed in full compliance with the protocol, Good Clinical Practices (GCP), and applicable regulatory requirements. All required study documentation will be archived as required by regulatory authorities.

Confidentiality Statement

This document is confidential. It contains proprietary information of Loxo Oncology, Inc. and/or Celerion. Any viewing or disclosure of such information that is not authorized in writing by Loxo Oncology, Inc. and/or Celerion is strictly prohibited. Such information may be used solely for the purpose of reviewing or performing this study.

1 PROTOCOL REVISION HISTORY

Date/Name	Description
22May2018 by PPD	
Final Protocol, Amendment 1
 
The protocol is amended following discussions during the site initiation visit. As a result of the amendment, the following sections of the protocol were updated (changes in strikethrough and additions in bold):
 
 1. Medical Affairs 360 LLC will no longer provide serious adverse event reporting services for this study. Therefore the contact information for serious adverse event reporting was updated in Section 3 Additional Key Contacts for the Study. 
 • Sponsor Contact Information for Serious Adverse Event Reporting Medical Affairs 360 LLC efax [contact] Email: [contact] Section 13.2.6.4 Serious Adverse Event was also updated. 2. In study Part 1 (itraconazole), Period 1 hematology, serum chemistry, coagulation test, and urinalysis for safety evaluation are to be performed on Day 7 instead of Day 8. During Period 2, these tests will not be performed on Day -4. These changes are reflected in Section 6 Study Events flow Chart, Table 1. In addition, the wording in footnote “h” was updated as follow: “Samples for serum chemistry will be obtained following a fast of at least 12 hours at screening and on Day 1 of both periods at check-in; at other scheduled times, serum chemistry tests will be performed after at least an 8-hour fast. However, in case of dropouts or rechecks and subsequent on study samples, subjects may not have fasted for 12 or 8 hours prior to the time that the serum chemistry sample is taken.” Section 13.2.5 Clinical Laboratory Tests was appropriately updated. 3. In study Part 2 (rifampin), Period 1 hematology, serum chemistry, coagulation test, and urinalysis for safety evaluation are to be performed on Day 7 instead of Day 8. During Period 2, these tests will not be performed on Day 1. These changes are reflected in Section 6 Study Events flow Chart, Table 2. In addition, the wording in footnote “h” was updated as follow: “Samples for serum chemistry will be obtained following a fast of at least 12 hours at screening and on Day 1 of Period 1 and Day 1 of Period 2 at other scheduled times at

	
check-in; at other scheduled times, serum chemistry tests will be performed after at least an 8-hour fast. However, in case of dropouts or rechecks and subsequent on study samples, subjects may not have fasted for 12 or 8 hours prior to the time that the serum chemistry sample is taken.”
 
Section 13.2.5 Clinical Laboratory Tests was appropriately updated.
 
4. The phrase “cut-off date” was replaced with “January 5, 2018” in Section 8.1.1 Clinical Background Information of LOXO-292. Additional minor updates were done throughout that section.5. In-text links to the package inserts containing full prescribing information for itraconazole and rifampin were updated throughout the protocol as appropriate.6. In Section 11 Study Population verbiage for sponsor approval for subject enrolment prior to dosing was updated as follows:
• The Sponsor will provide written approval of subjects for enrolment prior to dosing.7. In Section 11.2 Exclusion Criteria, criterion 7, the last bullet was corrected to correct the Study Period to Period 1 as this information was missing in the final protocol.8. In Section 11.4.2 Meals, wording was updated for Part 1 (Itraconazole), to remove the 1 hour and 30 minutes fast prior to itraconazole dosing in Period 2 other than on Day 1 The update to the protocol was as follows:
• For all doses in Period 2 other than on Day 1, subjects will be required to fast for at least 1 hour until 30 minutes prior to their scheduled morning dose, when they will be given a standard breakfast approximately 30 minutes prior to their scheduled morning dose. Subjects will fast for at least 2 hours following the dose.9. In Section 5 Synopsis and Section 12.1 Treatments Administered, the footnote demarcated by “*” under Part 1 (Itraconazole, Remaining subject n = 9), was updated to remove the provisional statement that an amendment will be performed for administration of a lower dose. Should a change in dose occur, appropriate processes will be followed. The update to the protocol was as follows:
• * Following completion of the sentinel group, the PI and Sponsor will review all pertinent safety and tolerability data from the sentinel group before proceeding to dose the remaining subjects. If the Sponsor opts to evaluate a lower
--	--

